#### ***6.2.4.6.3 Renal Function***

Fluid balance monitored at Baseline (Days 1 (Pre-dose) and then daily on Days 2 - 28 (Day 28 In or Out of ICU) will be numerically summarised (with the derived Last observation performed) using the actual values and change from baseline values by Treatment group (FP-1201-lyo/Placebo), Severity of ARDS (Moderate/Severe) and Overall for each assessment time using the FAS population.

#### ***6.2.4.7 Information from Externally Transferred Patients***

Observations recorded by site staff for patients who are externally transferred between Day 7 and Day 28 will be numerically summarised as this applies to only a subset of patients.

These data will be added to the 'Days free' endpoint scores and 'Length of stay' variables as appropriate for specific patients according to derivations specified in Section 5.9.4, Appendix 4.

#### ***6.2.4.8 Other Observations In The ICU***

Other notable Procedures, Interventions, Surgeries and Diagnostics which are recorded as free text during confinement in the ICU will be listed.

#### ***6.2.5 Efficacy Evaluations - Long Term/Extended Follow Up***

Assessments performed at Day 90 and Day 180 are considered Long term follow up and those at Day 360 an Extended follow up. These will only involve the FAS population.

##### ***6.2.5.1 Patient Status Analyses***

The Patient Status assessments of efficacy performed at Day 90, 180 and 360 will be categorically summarised by Treatment group and Severity of ARDS and Overall using the FAS population.

Details include: Alive/Dead, Location of death (ICU/Hospital), Date of death, Location if alive (ICU/Hospital) and Requirement for assisted ventilation. All are summarised and listed.

##### ***6.2.5.2 Quality Of Life Questionnaire Analyses***

The EQ-5D-3L is performed at Day 1 Pre-dose, Day 180 and Day 360. The EQ VAS score and sub scores will be numerically summarised for actual values and change from baseline by Treatment group (FP-1201-lyo/Placebo), Severity of ARDS (Moderate/Severe) and Overall for each assessment time using the FAS population only, although this sample will exclude any patients who did not survive to Day 180 or Day 360. Separate supporting summaries by Country will not be included.

The EQ VAS score will be analysed using an Analysis Of Covariance (ANCOVA) model as described for Total SOFA scores in Section 6.2.5.5. A separate analysis will be performed at each assessment time (Day 180 and Day 360) although p-values for inferential purposes will not be presented.

Sub scores will not be analysed.

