##### EQ-5D-3L Questionnaire

EQ-5D-3L provides a simple descriptive profile and a single index value of health status that can be used in clinical research and economic evaluation of healthcare as well as in population health surveys. The questionnaire is cognitively undemanding, designed for self-completion and takes only a few minutes to complete.

At the time when the patients are screened/enrolled in the study it may not be possible to directly obtain baseline information on their pre-admission QoL. In these cases, a description of the patient's pre-study functioning at home should be obtained from their relatives, recorded in the e-CRF and used as the reference value. This information will be checked by the patient at a later stage and correspondingly updated in the e-CRF.

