#### *8.5.2.5 Quality of Life, Respiratory and Neurological Functioning*

Health-related QoL, respiratory functioning (FEV1) and neurological functioning (6MWT) will be assessed at D180 (6 months) and included in the Clinical Study Report Addendum. Extended long-term follow-up data will also be gathered at D360 and submitted as an Addendum to the report (see Section 8.8.4).

The EQ-5D-3L data will be analysed overall. Summary statistics will also be provided in relation to the five individual domains. Further details will be provided in the SAP.

These data will only be available for survivors at D180. Analyses of these parameters will be based on the subset of patients who survive to that time point and not on the FAS. Only summary statistics and 95% CIs for treatment differences (for descriptive purposes) will be calculated.

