b These assessments will be done on the day the patient leaves the ICU, which will either be on D28 or earlier, according to the clinical progress of the patient. If the patient is still in the ICU on D28, the next visit or telephone contact will be at D90. If a patient leaves the ICU before D28, the survival status and other endpoints must be assessed on D28.

c D28 procedures apply for patients leaving the ICU before D28 and for patients withdrawing from the study before D28. For patients withdrawing from the study before D28 a sample should be taken for neutralising antibodies on the day they leave the ICU.

d D90 can either be a visit or telephone contact.

e Reconfirm inclusion/exclusion criteria before dosing, including that patient requires mechanical ventilation and is in the ICU (patients requiring ECMO after randomisation but before the first dose of IMP may still be included).

f Randomise after consent obtained and once eligibility criteria confirmed.

g Within 24 hours of ICU admission

h Within 1 hour pre-dose.

i Baseline EQ-5D-3L to be obtained from relatives and checked later with patient.

j For APACHE II scoring.

k Samples should be taken in the morning between 04:00 and 10:00.

l Medicines and therapies in previous month.

m Adverse events will be recorded after informed consent is obtained.

n Deaths are reported as SAE

o If it is possible to be performed by the investigator

Abbreviations: APACHE II=Acute Physiology and Chronic Health Evaluation; CD=cluster of differentiation; CT=computerised tomography; D=study day; ECG=electrocardiogram; ECMO=extra-corporeal membrane oxygenation; EQ-5D-3L=EuroQol 5-Dimensions 3-Level questionnaire; FEV1=forced expiratory volume in 1 second; GCS=Glasgow Coma Scale; ICU=intensive care unit; IFN=interferon; MxA=myxovirus resistance protein A; PaO2/FiO2=partial pressure of oxygen/fraction of inspired oxygen; PM=potential inflammatory marker; SOFA=Sequential Organ Failure Assessment; 6MWT=6-minute walk test;.

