### **5.4.2 Quality Of Life Evaluations**

General assessment of health is performed through a quality of life questionnaire (QOL). The EuroQol 5-Dimensions 3-Levels questionnaire (EQ-5D-3L) is administered at Day 1 Pre-dose, Day 180 and Day 360.

An EQ VAS score (ranging from 0-100) is measured (0= Worst imaginable health state, 100= Best imaginable health state) together with sub scores for Mobility, Self-care, Usual Activities, Pain/Discomfort and Anxiety/Depression. Each sub score ranges from 1 to 3 with 1 representing the best case and 3 the worst case.

The change from baseline (Day 1 Pre-dose) will be derived.

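### The supplied SAP text models only the EQ VAS, names no EQ-5D-3L index, and drops from the model survivors who have no baseline rating (minor)

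*SAP*

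**What the plan says.** **Protocol.** Section 6.1.2.6 describes the instrument: "EQ-5D-3L provides a simple descriptive profile and a single index value of health status". Section 8.5.2.5 states the analysis: "The EQ-5D-3L data will be analysed overall. Summary statistics will also be provided in relation to the five individual domains". It leaves further detail to the SAP, restricts the analysis to survivors at Day 180, and allows only summary statistics and descriptive confidence intervals. The protocol does not mention an EQ VAS.

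**SAP, measures.** Section 5.4.2 lists a VAS from 0 to 100 and five domain sub scores, and adds: "The change from baseline (Day 1 Pre-dose) will be derived". Section 6.2.5.2 summarises both but fits a model to the VAS alone, at Day 180 and Day 360, without p-values. The outputs listed in 7.2.5.2 (Tables 14.2.11.1 to 14.2.11.4 and two figures) cover the VAS and sub scores only.

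**SAP, model.** The sentence "The EQ VAS score will be analysed using an Analysis Of Covariance (ANCOVA) model as described for Total SOFA scores in Section 6.2.5.5" points to the Day 90 ventilation-free survival section, which uses a Cochran-Mantel-Haenszel test. The SOFA covariance model is in 6.2.4.5. It has change from baseline as response, with treatment, severity, country and baseline value as terms. Section 5.9.6 plans no imputation, and the EQ-5D-3L is not among its last-observation variables.

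**Baseline.** SAP Table 2, footnote i: "Baseline EQ-5D-3L to be obtained from relatives and checked later with patient". Protocol 6.1.2.6 turns to relatives where the patient cannot be asked directly, and has the e-CRF updated after the patient's check.

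**The concern.** Two things look incomplete.

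First, the protocol names one overall number from this questionnaire, the index. The SAP chooses a different overall number, the VAS, and gives no reason. A reader of the addenda would not learn how the index compares between arms, although the domain answers needed for it are collected.

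Second, a change-from-baseline model needs a baseline for every patient. Here that often means a relative being present and able to rate the patient's health before admission. Protocol 9.6.4 provides for patients who have no personal representative available, so some missing baselines should be expected. Such a patient may survive and answer fully at Day 180, by telephone if necessary (Protocol 6.1.2.6), and still be left out of the model. The later check by the patient has no visit in either schedule of procedures, and no rule covers ratings that are never checked.

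**Working it through.** The plan gives no figure on this point to reproduce. The check has four steps.

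**1. Does change rather than follow-up value matter?** Let Y be the follow-up score, B the baseline, T the treatment arm. The follow-up model is Y = a + τT + βB + error. Subtracting B from both sides gives Y − B = a + τT + (β − 1)B + error. The treatment coefficient τ is the same. So for patients with both values the choice makes no difference to the treatment estimate. It matters only for who can be included.

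**2. Does a relative's rating bias the comparison?** A simulation used assumed values: 210 survivors, baseline mean 75 and SD 18, follow-up = 40 + 0.4 × baseline + 5 × treatment + noise of SD 18, and 4,000 runs. The 210 is close to the planning figure in Protocol 8.10: 136 × 0.85 + 136 × 0.70 = 210.8 survivors at Day 28.

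| Error in baseline rating | Mean estimate (true value 5) | Standard error |
|---|---|---|
| none | 4.94 | 2.50 |
| SD 15, no shift | 4.98 | 2.59 |
| SD 15, shift −10 | 4.96 | 2.59 |

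The simulation error of each mean is about 2.5/√4000 = 0.04, so all three agree with 5. The two forms of the model differed by less than 10⁻¹³. Error that is equal in the arms costs about 4% in standard error (2.59/2.50 = 1.036) and causes no visible bias.

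**3. What does losing survivors cost?** The documents give no share without a baseline. If a fraction f is lost, equally in both arms, the standard error rises by 1/√(1 − f).

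| f (assumed) | Factor |
|---|---|
| 10% | 1/√0.9 = 1.054 |
| 20% | 1/√0.8 = 1.118 |
| 30% | 1/√0.7 = 1.195 |

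**4. How much would be recovered?** A retained patient without a baseline is not adjusted for it. With the values in step 2, that patient's residual variance is 18² + (0.4 × 18)² = 324 + 51.84 = 375.84, against 324. At f = 20% the average is 0.8 × 324 + 0.2 × 375.84 = 334.37, with SD 18.29. The standard error is then 18.29/18 = 1.016 times that with complete baselines, instead of 1.118. The corresponding factors are 1.008 at 10% and 1.024 at 30%. Under these assumptions most of the loss is avoided.

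**The case against.** The strongest reply is that the SAP does what the protocol allows. Protocol 8.5.2.5 speaks of the EQ-5D-3L data, not the index, and hands the detail to the SAP, which chose the VAS. The description in 6.1.2.6 is generic. This stands: a reader might infer a departure from the protocol, but the documents do not show one. Because the domains are listed separately and no other overall score is named, the index is the natural reading, but it remains an inference.

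Four further inferences should also be resisted.

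- *The domains are neglected.* They are summarised, which is all that 8.5.2.5 asks.
- *The economic evaluation loses its input.* Protocol 8.7 and SAP 5.5 and 6.2.6 work from service days and unit costs, and the optional cost-effectiveness plot uses VFDsurv. None of them uses the EQ-5D-3L.
- *A relative's baseline invalidates the treatment comparison.* It is to be checked by the patient, the analysis is confined to survivors, and step 2 shows no bias when error is equal in the arms. The remaining reservation is that an update made after treatment, by patients well enough to make it, is not guaranteed to be equal in the arms. Raw mean changes also need care in reading.
- *The index is never derived.* Appendix 4 (derivations) and Appendices 5 and 6 (Day 180 and Day 360 shells) were not supplied, and Protocol 8.8.4 mentions a separate SAP for this follow-up. What can be said is that the supplied text has no index and that 7.2.5.2 lists no output for one.

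It is also fair to say that scoring death goes beyond the survivor analysis in the protocol. That is why it is offered only as a supportive addition.

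**Conclusion.** The point holds in limited form and is minor. In the SAP text supplied, the VAS is the only EQ-5D-3L quantity modelled, no index or value set is named, and the model excludes survivors who have a follow-up score but no baseline rating.

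The number excluded is unknown. The 5% to 20% rise in standard error rests on an assumed 10% to 30% loss, equal in the arms and unrelated to outcome. It is an illustration, not an estimate for this trial. The absence of bias rests on rating error being the same in both arms.

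Consequences are limited: the endpoint is descriptive, has no p-values, lies outside the testing hierarchies in Protocol 8.5.2.1.1 and SAP 6.1.3, and appears only in the addenda. The case for change is that the gain is concrete and cheap. It keeps survivors in the model and supplies the overall measure that the protocol describes. It also adds a comparison not conditioned on survival. The VAS as defined in SAP 5.4.2 offers no clear place for death, because its zero is the worst imaginable health.

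**What to change.** In SAP 5.4.2 and 6.2.5.2:

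1. Derive the EQ-5D-3L index from the domain answers with one named value set. Analyse it alongside the VAS.
2. For both, take the Day 180 and Day 360 value as the response, adjusted for severity, country and baseline, with a missing-baseline indicator so that survivors without a baseline stay in.
3. Flag baselines rated only by a relative against those checked by the patient.
4. Add a supportive analysis over the FAS with death scored 0 on the index. Keep the survivor analysis as Protocol 8.5.2.5 specifies.
5. Correct the cross-reference from 6.2.5.5 to 6.2.4.5. The same wrong number appears in 6.2.5.3.1 and 6.2.5.3.2.
6. Add the index to the outputs in 7.2.5.2.

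The cost is SAP wording, a few extra outputs, and the choice of one value set for several countries, which is a compromise to be stated. No new patient data are needed, but it should be confirmed that the e-CRF or its audit trail (Protocol 9.1.1) identifies which baselines were checked or changed.

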### ***6.2.5.3 Respiratory And Neurological Function Assessment***

#### ***6.2.5.3.1 Respiratory Function (FEV-1) Analyses***

FEV-1 measured at Day 180 and Day 360 will be numerically summarised using actual values by Treatment group (FP-1201-lyo/Placebo), Severity of ARDS (Moderate/Severe) and Overall for each assessment time using the FAS population only. Again this group will only include survivors at the time of assessment. Separate supporting summaries by Country will not be included.

The FEV-1 will be analysed using an ANCOVA model (as for the Total SOFA scores in Section 6.2.5.5 but excluding the baseline covariate).

#### ***6.2.5.3.2 Neurological Function (6MWT) Analyses***

6MWT distances recorded at both Day 180 and Day 360 will be numerically summarised using actual values by Treatment group (FP-1201-lyo/Placebo), Severity of ARDS (Moderate/Severe) and Overall for each of the performed tests (Test One/Test Two). They will also be summarised according to the furthest distance walked during Test One or Test Two as recommended by the 6MWT guidelines (Ref 11). Separate summaries by Country will not be included.

These will involve patients from the FAS population who survive up to the time of assessment.

In line with the guidelines the furthest distance walked during the two tests will be analysed using an ANCOVA model (similar to the Total SOFA scores in Section 6.2.5.5 excluding the baseline covariate). As described in Section 5.4.3.2, in cases where only one result is collected this will also be used as the best result (furthest distance walked). The value of inclusion of additional Pre-Test covariates such as Walking limitations, Supplemental Oxygen use, SP02, Dyspnoea or Fatigue will be explored.

In addition, the distance walked during Test One will also be performed as a supplemental analysis in case there is a disproportionate number of patients across the two treatment groups who refuse or who are unable to perform the second test and which may lead to inconsistent inclusion of a possible 'learning effect'.

As the 6MWT is likely to only be performed in what is effectively a selective subgroup of patients (i.e.: those who survive) the results will be assessed in conjunction with the mortality rates in the two treatment groups. The LS mean and the 95% confidence interval for the treatment difference in those LS means will therefore only be presented Overall.

All other measures will only be summarised.

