#### 6.1.2.6 Quality of Life, Respiratory Functioning and Neurological Functioning

Health-related QoL (EQ-5D-3L), respiratory functioning via FEV1 and neurological functioning via the 6MWT, will be assessed at D180 (6 months). If the patient is unable to come to the hospital for the FEV1 and 6MWT assessments, the QoL information should still be obtained by telephone interview. Additional data will be collected at D360 (12 months) to form part of the extended long-term follow-up.

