### Six-minute Walk Test

The 6MWT measures (Ref: Holland et al 2014) the distance that a patient can quickly walk on a flat, hard surface in a period of 6 minutes. According to the current standard the test should be done twice and the best result is used. It evaluates the global and integrated responses of all systems involved during exercise, including the pulmonary and cardiovascular systems, systemic circulation, peripheral circulation, blood and neuromuscular units and muscle metabolism. The self-paced 6MWT assesses the sub-maximal level of functional capacity and may better reflect the functional exercise level for daily activities.

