**Validity of 6MWD**

There is a large body of data demonstrating construct and criterion validity for the 6MWD in individuals with chronic respiratory disease [1]. Relationships are strongest with measures of maximal exercise

TABLE 1 Methods checklist

	Yes	No
Panel assembly		
Included experts for relevant clinical and nonclinical disciplines	X	
Included individual who represents the views of patients and society at large		X
Included methodologist with appropriate expertise	X	
Literature review		
Performed in collaboration with a librarian	X	
Searched multiple electronic databases	X	
Reviewed reference lists of retrieved studies	X	
Evidence synthesis		
Applied pre-specified inclusion and exclusion criteria	X	
Evaluated included studies for sources of bias	X	
Explicitly summarised benefits and harms	X	
Used PRISMA1 to report systematic review		X
Used GRADE to describe quality of evidence		X
Generation of recommendations		
Used GRADE to rate the strength of recommendations		NA

PRISMA: Preferred Reporting Items for Systematic Reviews and Meta-Analyses; GRADE: Grading of Recommendations Assessment, Development and Evaluation; NA: not applicable.

performance and physical activity (correlation coefficients 0.4–0.93). Relationships between 6MWD and respiratory function (forced expiratory volume in 1 s (FEV1), forced vital capacity and diffusing capacity of the lung for carbon monoxide (DLCO)) (correlation coefficients 0.31–0.55) or health-related quality of life (HRQoL) (correlation coefficients 0.03–0.65) are of weak to moderate strength across all disease groups examined.

Direct comparisons of the physiological demands of the 6MWT and CPET show that although measures of peak exercise performance ( $V\dot{O}_{2\text{peak}}$  and heart rate (HR) peak) are similar between the tests, the 6MWT has substantially lower ventilatory requirements (peak carbon dioxide production, peak ventilation and respiratory exchange ratio) [3–8], which may contribute to its tolerability in adults with chronic respiratory disease. Overall, these data lend support to the conceptualisation of the 6MWT as a test of functional exercise capacity.

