Over the past 10 years, a number of new estimates of the MID for 6MWD have been published. Our systematic review [1] identified 11 studies, in COPD (six studies), ILD (three studies) and PAH (two studies). The majority of MID estimates from these studies are based on distribution-based methods (using statistical properties of the measure), rather than anchor-based methods (where change in 6MWD is related to another clinically important marker of change). Most values were generated for individuals with COPD participating in a rehabilitation programme rather than pharmacotherapy. The median estimate across all studies was 30 m [1]. There is currently little evidence to suggest that the MID varies according to patient characteristics, including the type of chronic lung disease or the baseline 6MWD. Most MID estimates were generated using group mean data and are best used to interpret group mean changes in 6MWD [65–67]. However, studies that derived the MID using methodologies that are applicable to individuals reported similar MID estimates [68, 69]. More studies are required to explore the magnitude of important changes in 6MWD with different interventions and to establish the MID in other chronic respiratory diseases.

In summary, the available evidence suggests a MID of 30 m for adult patients with chronic respiratory disease. There is some variability across studies and methods to determine the MID; however, based on the large evidence base now available, we can be confident that the MID lies between 25 and 33 m.

*Responsiveness of the 6MWD*

Few studies have been explicitly designed to assess the responsiveness of 6MWD to treatment effects, but a large number of randomised trials provide insights in this area. We chose the Cochrane reviews on exercise interventions for COPD [70, 71] and ILD [72] and the Cochrane review on endothelin receptor antagonists in PAH [73] to investigate the responsiveness of 6MWD to interventions of known efficacy. The meta-analyses for 6MWD showed highly statistically significant improvements in 6MWD, with effects between 34 and 78 m and effect sizes between 0.38 and 1.07 [1]. The standardised response means (mean change/standard deviation of change) ranged from 0.2 to 1.2 [1]. The 6MWD therefore appears to be responsive to treatment effects in patients with COPD, ILD and PAH. It should be noted that most of these values have been generated from rehabilitation-based studies.

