### ***5.9.6 Strategy For Missing Data***

No biases resulting from missing data are anticipated and, as a consequence No imputation of any missing values at any of the assessments performed is planned.

However, to allow for patient attrition or any changes to the scheduled patient assessments as a consequence of the treatment response a 'Last observation performed' assessment will be derived for specific Short term efficacy (Ventilation assessment, System Organ Failure (SOFA), Cardiovascular, Pulmonary and Renal function), Pharmacodynamic (IFN $\beta$  ADA & Nab, MxA, CD73, PIM) and Safety variables (Vital signs and Laboratory assessments). This approach will use the last available non-missing post baseline value.

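### The 6-minute walk analysis compares only survivors who could be tested, has no rule for survivors unable to walk, and labels the result neurological functioning

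*SAP*

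**What the plan says.** **Population and model.** SAP 6.2.5.3.2 fits an ANCOVA without a baseline term to the furthest distance walked, at D180 and at D360. On who is analysed it says: "These will involve patients from the FAS population who survive up to the time of assessment". It then notes that "the 6MWT is likely to only be performed in what is effectively a selective subgroup of patients (i.e.: those who survive" and says the results will be read together with mortality in the two arms. Death is the only selection it names.

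**Inability.** The one provision concerns the second walk. A supplementary analysis of Test One is planned in case the arms differ in patients "who refuse or who are unable to perform the second test". Nothing is said about a survivor who cannot do the first.

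**Attendance and suitability.** Protocol 6.1.2.6 says that if a patient cannot come to hospital for FEV1 and the walk, "the QoL information should still be obtained by telephone interview". Protocol 7.2.9 and 7.2.10 likewise fall back on telephone contact. SAP 5.4.3.2 places a suitability assessment, with contraindications, before the walk.

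**Missing data.** SAP 5.9.6 expects no bias from missing data and states: "No imputation of any missing values at any of the assessments performed is planned". The walk is not among the variables given a last-observation derivation.

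**Label.** The protocol objectives (2.2.2), the variable list (6.1) and the SAP headings call the test a measure of neurological functioning. Protocol 6.1.2.6 and SAP 5.4.3.2 describe it as the combined response of all the body systems used in exercise, and the protocol adds: "The self-paced 6MWT assesses the sub-maximal level of functional capacity".

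**The concern.** Taken alone, the population sentence covers every survivor. Taken with the rules on attendance, suitability and imputation, it covers only survivors fit enough to be tested. Being testable is itself an outcome that treatment could change, in either direction:

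- If treatment saves frail patients who cannot walk at D180, they are alive, have no distance, and leave the model.
- If treatment restores some walking to patients who otherwise could not walk, they enter the active arm, probably with short distances, and pull its mean down.

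Reading the result beside mortality addresses selection by death. It does not address inability among the living.

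The label is a second, smaller matter. A distance in metres would be reported under a secondary objective on neurological functioning, although the documents describe the test as a measure of something broader.

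**Working it through.** **1. Who has a distance?** Following a survivor through the plan:

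| Survivor at D180 or D360 | What the plan obtains | Enters the ANCOVA? |
|---|---|---|
| Attends, suitable, walks once or twice | Distance | Yes |
| Attends, fails the suitability check | Reason may be recorded; no distance | No |
| Attends, cannot walk | No distance; no 0 m or worst-rank rule | No |
| Cannot attend | Telephone information including QoL | No |

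Protocol 8.2.1.4 allows last observation carried forward for other efficacy analyses. It cannot help at D180, because no earlier walk exists. At D360 a D180 distance may exist, but the SAP does not carry it forward.

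**2. Is there a figure to reproduce?** No. Neither document gives an expected distance, SD, effect size or non-testing rate for the walk. Everything below is illustration. The only document inputs are 300 patients randomised 1:1 and the planned D28 mortality of 30% and 15% (Protocol 8.10).

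**3. Approximate size of the analysed set.** With 150 per arm and later deaths ignored, survivors number 150 x 0.85 = 127.5 on active and 150 x 0.70 = 105 on placebo. If 10% to 40% of survivors are not tested (assumed, equal in both arms):
- active: 127.5 x 0.90 = about 115, down to 127.5 x 0.60 = about 77
- placebo: 105 x 0.90 = about 95, down to 105 x 0.60 = 63

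**4. What the planned contrast can miss.** Let M be the mean among walkers and u the proportion of survivors unable to walk. With inability scored as 0 m, the all-survivor mean is (1 - u) x M. If M is equal in the arms, the planned contrast is 0 m and the all-survivor contrast is M x (u_placebo - u_active). With 30% against 20% unable (assumed), whichever arm is worse:
- M = 350 m: 350 x 0.10 = 35 m
- M = 400 m: 40 m
- M = 450 m: 45 m

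**5. What happens to a real difference in walking ability.** Suppose underlying distance is normal, with a placebo mean of 350 m, and survivors below a threshold c are not tested (all assumed). The mean among those tested is mu + sd x phi(a) / (1 - Phi(a)), with a = (c - mu) / sd.

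| SD, threshold | True difference 30 m | True difference 50 m |
|---|---|---|
| 150 m, 200 m | 19.8 m | 33.9 m |
| 120 m, 200 m | 22.1 m | 38.0 m |
| 150 m, 150 m | 22.6 m | 38.6 m |

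In these cases the tested-only contrast recovers about two thirds to three quarters of the difference.

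**6. Could the arms differ in inability?** Planned mortality leaves an extra 15% of the active arm alive. Assume 20% of placebo survivors, and 20% of active patients who would have survived anyway, are unable to walk.
- If all the extra survivors are unable: (0.70 x 0.20 + 0.15) / 0.85 = 34%.
- If half are unable, and 20% of the rest: (0.70 x 0.20 + 0.075 + 0.075 x 0.20) / 0.85 = 27%.

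So a drug that works on mortality could itself produce the imbalance.

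**7. Label.** The technical standard reproduced in Protocol Appendix 2 concludes that "these data lend support to the conceptualisation of the 6MWT as a test of functional exercise capacity". That agrees with the test descriptions in Protocol 6.1.2.6 and SAP 5.4.3.2, and not with the name given to the endpoint.

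**The case against.** The strongest reply is that little depends on this analysis. Protocol 8.5.2.5 restricts these outcomes to survivors and to summary statistics with descriptive confidence intervals. The walk is in neither testing hierarchy (Protocol 8.5.2.1.1, SAP 6.1.3) and is reported only in the D180 and D360 addenda. This stands, and it sets the weight of the point.

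The second reply is that the non-testing would be visible. Continuous summaries give n (SAP 6.1), survival status is tabulated by arm (SAP 6.2.5.1), pre-test evaluations are summarised (SAP 7.2.5.3.2), and the EQ-5D-3L mobility item is summarised by arm and can be collected by telephone. The table shells in SAP Appendices 5 and 6 are not in the text available, so a not-done row cannot be ruled out. This stands in part: a careful reader could derive how many were not tested, and part of the reason. It leaves the reported treatment difference unchanged.

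The third reply concerns the remedy. Making a ranking with deaths below 0 m the main comparison would bring the dead back into an analysis that Protocol 8.5.2.5 confines to survivors. With planned mortality of 30% against 15%, it might largely repeat the mortality result. This stands, and such a ranking should be exploratory at most.

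A reader might also set the illustrated 35-45 m against the statement in Appendix 2 that "the available evidence suggests a MID of 30 m for adult patients with chronic respiratory disease" and infer a clinically important hidden effect. The documents do not support that. The inputs are assumed. The standard says it is not intended for people without chronic respiratory disease. Its 30 m refers to changes in walked distance, not to means that contain scored zeros.

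**Conclusion.** The point holds, with modest weight. As written, the plan estimates the walk difference among tested survivors while recognising selection by death only. That estimate can miss, or be biased by, a difference between arms in inability to walk. If inability is equal in the arms and walker means are equal, nothing is lost. With a 10-point difference and equal walker means of 350-450 m, 35-45 m is missed. The actual size and direction cannot be known from the documents.

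Three stronger readings are tempting and do not follow:

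- *That the SAP expressly excludes survivors who cannot walk.* It does not. The exclusion results from attendance, the suitability check, the lack of imputation and the absence of a rule.
- *That an efficacy conclusion of the trial is at risk.* The endpoint is descriptive and outside the formal testing.
- *That the protocol itself says the test cannot isolate neurological function.* No such statement appears, and neuromuscular units are among the systems it lists. What the text supports is narrower: the test is a global measure, so a walk result should not be reported as evidence on neurological function specifically.

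Scoring inability as 0 m also leaves one problem in place. The comparison is still among survivors, and treatment may change who survives, so it must still be read beside mortality.

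**What to change.** 1. **Tabulate by arm at D180 and D360:** dead; alive and unable for medical or physical reasons; alive and not tested for other reasons (refusal, non-attendance); tested.
2. **Add a supplementary descriptive analysis in survivors** to SAP 6.2.5.3.2, scoring medical or physical inability as 0 m and giving the treatment difference with a rank-based or bootstrap 95% CI. Refusal and non-attendance alone should not be scored 0 m. Keep the planned LS means and describe them as applying to those tested. An ordering with deaths below 0 m is optional and exploratory only, given Protocol 8.5.2.5.
3. **Confirm that the reason for not testing is recorded.** The 6MWT evaluation form behind Listing 16.2.2.10 is the likely source, but its content is not shown and nothing says it is completed for telephone contacts.
4. **Label the outcome functional exercise capacity** in the objectives, SAP and reports, and draw no conclusion on neurological function from it.

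While editing, correct the cross-reference in SAP 6.2.5.3.2, which sends the reader to 6.2.5.5 for the SOFA model when it is in 6.2.4.5. Also reconcile SAP 7.2.5.3, which mentions a baseline assessment, with 5.4.3.2, which says a baseline is not appropriate.

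**Cost:** one table, one supplementary analysis, some data checking and wording changes. No new visits are needed.
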